8.4 Method and duration of follow-up of the study subjects after adverse reactions

Information on all newly developed/continuing ARs is recorded at each next/unscheduled visit. In case of repeated report on continuing AR, it is necessary to complete a new template of AR Report Form with note of date of a primary report on continuing AR.

All ARs should be traced until their resolution or until the Investigator considers them as “chronic” or “stable” (AR outcomes in such cases are classified as resolving/resolved with sequelae/ not recovered). Information on this should be recorded in the primary documentation, CRF of a female patient and the final AR Report Form.

At the final visit (Visit 3), the Investigator instructs the study subject on necessity to report on any ARs subsequently which, in the opinion of a female patient or her physician may be related to the administration of the test drug/reference drug.

8.5 Modification of the study drug dosage regimen

In the present study, modification of the study drug dosage regimen is not considered which is provided by the purposes and design of the present study.

9 Statistics

9.1 Description of statistical methods to be used, including terms of each planned interim analysis

Statistical analysis will be performed using a specialized software, selection of which will be performed at the stage of preparation of statistical analysis plan.

Continuous (quantitative) data will be presented using a number of observations, arithmetic mean, 95 % confidence interval (CI) for the mean (unless otherwise specified), standard (mean square) deviation, median, interquartile range, minimum and maximum.

Serial, categorical and qualitative data will be provided using absolute frequency (number of observations), relative frequencies (percent) and 95 % CI (unless otherwise specified).

Unless otherwise specified, in the plan of statistical analysis, statistical test will be bilateral with 5% confidence level.

Anamnesis and ARs will be coded using MedDRA classifier.

This section briefly describes the planned analysis. A complete analysis will be described in the plan of statistical analysis.

9.1.1 Demographic data, baseline data and follow-up data

Demographic characteristics, characteristics of baseline level and follow-up, such as anamnesis (classified according to MedDRA) and concomitant drugs will be described by treatment groups for ITT population and then for safety, if they are different (see section 9.7).

9.1.2 Analysis of main efficacy parameters

Main efficacy parameter in the given study is achieving clinical efficacy of the drug defined as:

- Frequency of reducing number of adhesions after repeated MRI by 3 or more (in female patients with 10 and less adhesions at the baseline) or by 30% and more (in patients with >10 adhesions at the baseline)) in comparison to baseline MRI data

Considering that the given analysis will be performed in the confirmation form of superiority over placebo hypothesis (superiority testing), unilateral statistical criteria will be used, and the level of significance will be established at 5%. For differences between each dose of the drug Seroguard and the placebo, a bilateral 95% binominal accurate confidence interval will be calculated for percentage difference. Superiority will be confirmed, if the lower limit of the confidence interval will exceed 0.05 (5%).

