Using these baseline data, the following assumptions were introduced (as per the method specified in the FDA Guidance for Industry: Non-Inferiority Clinical Trials):

- The study will be conducted as a *superiority trial*, i.e. at least one dosage of Seroguard must be more efficient than the placebo, whereby the *superiority margin* will be 5% and more (definition of endpoint and superiority margin from the main study of Adept[®] was used). Comparison with placebo will be performed for each dosage of the drug separately. Comparison of dosages by efficacy between them is not planned and will be a subject of the study in the Phase III of clinical studies of the drug
- Expected rates of achieving the primary endpoint in the groups with different dosages will be considered initially equal
- First type error (α) = 5 % (0.05) for *superiority* hypothesis
- Second type error (β) = 20 % (0.2), that corresponds to 80 % power.
- Expected withdrawal from the study will make 15% at screening and 10% after randomization

Null and alternative hypotheses for the *superiority testing* stage are worded as follows:

1. Null hypothesis (H_0) holds that the difference in the rate of the primary endpoint achievement for one of the dosages of the drug Seroguard and the placebo will not exceed 5% in favor of the drug

$$H_0: p_1 - p_0 \leq 0.05$$

2. Alternative hypothesis (H_A) holds that the difference in the rate of the primary endpoint achievement of one of the dosages of the

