- Expected rates of achieving the primary endpoint in the groups with different dosages will be considered initially equal
- First type error (α) = 5 % (0.05) for *superiority* hypothesis
- Second type error (β) = 20 % (0.2), that corresponds to 80 % power.
- Expected withdrawal from the study will make 15% at screening and 10% after randomization

Null and alternative hypotheses for the *superiority testing* stage are worded as follows:

1. Null hypothesis (H_0) holds that the difference in the rate of the primary endpoint achievement for one of the dosages of the drug Seroguard and the placebo will not exceed 5% in favor of the drug

$$H_0: p_1 - p_0 \leq 0.05$$

2. Alternative hypothesis (H_A) holds that the difference in the rate of the primary endpoint achievement of one of the dosages of the drug Seroguard and the placebo will exceed 5% in favor of the drug

$$H_A: p_1 - p_0 > 0.05$$

Where p_0 and p_1 are the rates of the primary endpoint achievement in the groups of the placebo and Seroguard (of any dosage), respectively.

For the purpose of calculation of the sample size in each group in this case, the formula is applied which is given in (33)

$$n = (p_1 \times (1 - p_0) + p_0 \times (1 - p_0)) \times \left(\frac{z_{1-\alpha} + z_{1-\beta}}{p_1 - p_0 - \delta} \right)^2$$

where

n is the size of one group;

z is the value of the normal distribution function with the given α and β levels;

δ is superiority margin - 5%;

p_1 is the expected percentage in the active drug group (one of the dosages) – 45%

p_0 is the expected percentage in the placebo group – 5%

Applying the above data into this formula, we obtain the minimum number of patients in the placebo group without considering withdrawal: 24 completed cases which corresponds to 26 randomizations and 30 screenings.

Thus, the total number to be enrolled in the study is:

- 1) Placebo group, 1.5 mL/kg – up to 30 screened female patients that corresponds to 26 randomizations and 24 completed cases
- 2) Placebo group, 2.4 mL/kg – up to 30 screened female patients that corresponds to 26 randomizations and 24 completed cases
- 3) Seroguard group, 1.5 mL/kg – up to 30 screened female patients that corresponds to 26 randomizations and 24 completed cases
- 4) Seroguard group, 2.4 mL/kg – up to 30 screened female patients that corresponds to 26 randomizations and 24 completed cases

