9.3 A significance level used

In all the tests, a 5% significance level will be used, whereby a primary endpoint will be analyzed using unilateral test, and bilateral statistical tests will be used for analysis of secondary endpoints.

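### Section 9.1.2 sets the primary superiority decision at two levels (one-sided 5% test, two-sided 95% confidence limit), and the 24 per group was calculated for the looser one

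*Protocol*

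**What the plan says.** Section 9.1.2 says of the primary endpoint that "unilateral statistical criteria will be used, and the level of significance will be established at 5" per cent. Section 9.3 repeats this for the whole study: "a 5% significance level will be used, whereby a primary endpoint will be analyzed using unilateral test".

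The same paragraph of 9.1.2 then gives the success criterion for each dose against placebo: "a bilateral 95% binominal accurate confidence interval will be calculated for percentage difference. Superiority will be confirmed, if the lower limit" of the interval is greater than 0.05.

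The sample size, in the Synopsis and section 9.2, uses "First type error (α) = 5 % (0.05") and "Second type error (β) = 20 % (0.2), that corresponds to 80 % power". Alpha enters the formula as z(1−α), not z(1−α/2), and the key reads "z is the value of the normal distribution function with the given α and β levels". The margin is 5% and the expected rate on drug is 45%. The result is: "we obtain the minimum number of patients in the placebo group without considering withdrawal: 24 completed cases".

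The placebo rate is 10% in the Synopsis, and the text of 9.2 says no more than 10%. The parameter list in 9.2 instead has "expected percentage in the placebo group – 5" per cent.

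**The concern.** The two sentences in 9.1.2 are different decision rules. A result with a one-sided p-value against the 5% margin between 0.025 and 0.05 is significant at the stated level but fails the interval criterion. Anyone reporting such a result could find text in the protocol for either conclusion, in an analysis the protocol itself presents as confirmatory.

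The planned size is also tied to one rule while success is declared by the other. The stated 80% power then does not describe the chance of meeting the written success criterion.

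**Working it through.** **Inputs.** Rate on drug p1 = 0.45, margin δ = 0.05, power 80% (z = 0.8416), 24 completers per group (section 9.2). Placebo rate p0 = 0.10 (Synopsis) or 0.05 (parameter list in 9.2). One-sided 5% means z = 1.645; the lower limit of a two-sided 95% interval means z = 1.960.

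**Step 1: which level gives 24?** n = V × ((z + 0.8416)/(p1 − p0 − δ))². The standard variance is V = p1(1−p1) + p0(1−p0). The formula as printed has p1(1−p0) as its first term, so both forms are shown.

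| Variance | p0 | V | n at z = 1.645 | n at z = 1.960 |
|---|---|---|---|---|
| Standard | 0.10 | 0.3375 | 23.18 | 29.43 |
| Standard | 0.05 | 0.2950 | 14.89 | 18.90 |
| As printed | 0.10 | 0.4950 | 34.00 | 43.17 |
| As printed | 0.05 | 0.4750 | 23.97 | 30.43 |

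For example, 0.3375 × ((1.645 + 0.8416)/0.30)² = 23.2, rounded up to 24. The plan's figure is reproduced by two routes, both at one-sided 5%. No combination gives 24 at one-sided 2.5%.

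**Step 2: power per comparison at 24 v 24.** By formula, power = Φ((p1 − p0 − δ)/√(V/n) − z) with the standard V. At p0 = 0.10, 0.30/√(0.3375/24) = 2.530. Then Φ(2.530 − 1.645) = 81.2% and Φ(2.530 − 1.960) = 71.6%. The exact column enumerates all 25 × 25 outcomes. It uses a score-ordered exact unconditional p-value, maximised over the nuisance rate, with each tail treated separately.

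| p0 | One-sided 5%: formula / exact | 95% interval rule: formula / exact |
|---|---|---|
| 0.10 | 81.2% / 78.6% | 71.6% / 68.4% |
| 0.07 | 89.4% / 87.7% | 82.4% / 79.9% |
| 0.05 | 93.5% / 92.6% | 88.4% / 86.7% |

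If all 26 randomized per group are evaluable and p0 = 0.10, the figures are 83.8% / 81.3% at one-sided 5% and 75.0% / 70.7% under the interval rule.

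**Step 3: how often do the rules disagree?** At 24 v 24, 19 outcome tables have an exact one-sided p above 0.025 and at most 0.05. Their total probability is 10.2% at p0 = 0.10 and 5.8% at p0 = 0.05, per comparison.

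**Step 4: one such table.** With 10/24 on drug and 3/24 on placebo the observed difference is 29.2 percentage points. The exact one-sided p against the 5% margin is 0.0373, so the test at 5% rejects. The exact 95% lower limit lies between 3.0% and 3.25%, so the interval rule does not confirm superiority. The exact 90% lower limit lies between 6.25% and 6.5%, in agreement with the test.

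**The case against.** The strongest reply is that only one sentence in 9.1.2 says what confirms superiority, and it is the interval sentence; the one-sided 5% statement names no statistic. On that reading 10/24 against 3/24 is simply not confirmed. The stricter rule also cannot make a false claim easier: at p0 = 0.10 its exact type I error is 0.017, against 0.041 for the 5% rule. This is true, and it means the harm lies in clarity and power and not in false positives. But 9.1.2 and 9.3 both fix the level for the primary endpoint explicitly, and the sample size is built on it, so the statement cannot be read as idle. The general defaults in section 9.1 do not settle it, because they give way where something else is specified.

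The power loss is also conditional, and this stands.

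- **Placebo rate.** The text of 9.2 treats 10% as a ceiling. At 7% the interval rule has about 80% power, and at 5% it has more.
- **Trial aim.** The sample size section asks for success on at least one dose. If both doses reach 45% and each has its own placebo group, power under the interval rule at p0 = 0.10 is 1 − (1 − 0.684)² = 90%.
- **Comparator and interval type.** The protocol does not say whether the two placebo groups are pooled, or which exact interval is meant. With 24 v 48 at p0 = 0.10, interval-rule power is 77.6% by formula and 71.4% with the tail-based exact interval. It is 81.5% if the interval inverts a single two-sided score test. At 24 v 24 this choice hardly matters (68.4% against 68.5%).

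None of this reconciles the two levels.

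**Conclusion.** The concern holds. Section 9.1.2 sets one-sided 5% and one-sided 2.5% for the same decision, and the 24 per group follows only from the former. That conclusion needs no assumption about the placebo rate, the variance term, the comparator or the type of interval.

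The size of the consequence does depend on them. With own-volume placebo, 24 completers per group and 45% on drug, moving from the 5% level to the interval rule costs about 10 points of power per comparison at a 10% placebo rate, down to 71.6% by formula or 68.4% exact. At about 7% power is close to 80%, and at 5% it is above. Power for at least one dose remains about 90% at a 10% placebo rate, under the conditions given above. The protocol claims no control of error across the two doses, and no breach of such control is alleged. The point must be settled before unblinding, because it decides what counts as success.

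**What to change.** State one rule, and reconcile the placebo rate (10% or 5%) at the same time so that the power can be quoted. Check the first variance term against the cited source too: p1(1−p1) is the standard form.

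- **Option A: keep one-sided 5%.** Base success on the lower limit of a two-sided 90% exact interval. This agrees with alpha in the Synopsis, 9.1.2, 9.2 and 9.3. The 24 per group stays, with 81.2% power by formula and 78.6% exact at a 10% placebo rate, so the exact figure is slightly under 80%. The change is 95% to 90% in the interval wording of 9.1.2.
- **Option B: keep the two-sided 95% interval.** Change alpha to one-sided 2.5% in the Synopsis, 9.1.2, 9.2 and 9.3, and restate per-comparison power at 24 completers with own-volume placebo. That is about 72% by formula and 68% exact at a 10% placebo rate, or about 88% and 87% at 5%.

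Both options are wording changes and neither adds patients. Should the sponsor want 80% per comparison under Option B at a 10% placebo rate, that would take 30 completers per group by formula, or 34 with a score-based exact interval (30 gives 75.9%).

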	
drug Seroguard and the placebo will exceed 5% in favor of the drug
 $H_A: p_1 - p_0 > 0.05$ 
Where p_0 and p_1 are the rates of the primary endpoint achievement in the groups of the placebo and Seroguard (of any dosage), respectively.
 
For the purpose of calculation of the sample size in each group in this case, the formula is applied which is given in Chow S, Shao J, Wang H. 2008. Sample Size Calculations in Clinical Research. 2nd Ed. Chapman & Hall/CRC Biostatistics Series. page 90
 $n = (p_1 \times (1 - p_0) + p_0 \times (1 - p_0)) \times \left(\frac{z_{1-\alpha} + z_{1-\beta}}{p_1 - p_0 - \delta} \right)^2$ 
where
 
n is the size of one group;
 
z is the value of the normal distribution function with the given α and β levels;
 
δ is superiority margin 5%;
 
p_1 is the expected proportion in the active drug group (one of the dosages) – 45%
 
p_0 is the expected proportion in the placebo group – 10%
 
Applying the above data in this formula, we obtain the minimum number of patients in the placebo group without considering withdrawal: 24 completed cases which corresponds to 26 randomizations and 30 screenings.
 
Thus, the total number to be enrolled in the study is:
 
 1) Placebo group, 1.5 mL/kg – up to 30 screened female patients that corresponds to 26 randomizations and 24 completed cases 2) Placebo group, 2.4 mL/kg – up to 30 screened female patients that corresponds to 26 randomizations and 24 completed cases 3) Seroguard group, 1.5 mL/kg – up to 30 screened female patients that corresponds to 26 randomizations and 24 completed cases 4) Seroguard group, 2.4 mL/kg – up to 30 screened female patients that corresponds to 26 randomizations and 24 completed cases
--	---

	Thus, total of 120 female patients are to be screened and at least 104 female patients are to be randomized for the study.
--	--

Acronyms

ALT	Alanine Aminotransferase
Ap	Alkaline Phosphatase
APTT	Activated Partial Thromboplastin Time
AR	Adverse Reaction
ASA	American Association of Anaesthetists
AST	Aspartate Aminotransferase
ATC	Anatomical Therapeutic Chemical Classification System
BP	Blood Pressure
CI	Confidence Interval
CRF	Case Report Form
CRO	Contract Research Organization
DP	Drug Product
ECG	Electrocardiography
ESR	Erythrocyte Sedimentation Rate
FDA	Food and Drug Administration
FL	Federal Law
GCP	Good Clinical Practice
GGTP	Gamma-Glutamyl Transpeptidase

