9.2 Planned number of the study subjects

In the studies of the drug Adept[®] (Innoventica plc), maximally close to the test drug by mechanism of action, a primary endpoint was used. It was determined as a decrease in number of adhesions during second look diagnostic laparoscopy by 3 or more (in patients with 10 or less adhesions at the baseline) or by 30% and more (in patients with >10 adhesions at the baseline) is 45%.

Performance of second look laparoscopy under the present study is unacceptable from the ethical point of view, MRI will be used for evaluation of the primary end point. As per the publication (21), MRI data highly correlate with laparoscopy picture (both pre-surgical and post-surgical studies during repeated laparoscopies). The exclusions are the thinnest adhesions that may not be seen on MRI which may be compensated by use of high-field MRI. Hence, MRI allows to visualize adhesions qualitatively and quantitatively and to obtain data with the same degree of detalization as during laparoscopic investigation before and after the surgery.

Thus, calculation of sample size will be based on efficacy of similar drugs studied based on laparoscopic data, however, MRI control will be used in the study, first of all due to ethical considerations and due to strong correlation between MRI data and laparoscopy data.

Accordingly, as per the above studies of the drug Adept[®] (20), efficacy related to achieving the primary end point (clinical efficacy determined as a decrease in number of adhesions during second look diagnostic laparoscopy by 3 and more (in female patients with 10 or less adhesions at

the baseline) or by 30% and more (in patients with > 10 adhesions at the baseline)) is 45%. In the control group (placebo) based on literature review and meta-analysis (31) achieving clinical efficacy is recorded in not more than 10% cases.

Using these baseline data, the following assumptions were introduced (as per the method specified in (32)):

- The study will be conducted as a *superiority trial*, i.e. at least one dosage of Seroguard must be more efficient than the placebo, whereby the *superiority margin* will be 5% and more (definition of endpoint and superiority margin from the main study of Adept® was used). Comparison with placebo will be performed for each dosage of the drug separately. Comparison of dosages by efficacy between them is not planned and will be a subject of investigation in the Phase III of clinical studies of the drug

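### The 80% power in 9.2 comes from a z formula, but 9.1.2 decides by an unspecified exact interval; the constructions that fit differ by 16 to 20 points of power at 24 per group

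*Protocol*

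**What the plan says.** Sizing (protocol 9.2, repeated in the synopsis) uses the unpooled normal-approximation formula with a one-sided quantile. The error rates are "First type error (α) = 5 % (0.05) for *superiority* hypothesis" and "Second type error (β) = 20 % (0.2), that corresponds to 80 % power". The active rate "is the expected percentage in the active drug group (one of the dosages) – 45" per cent. For placebo, the 9.2 text says that "achieving clinical efficacy is recorded in not more than 10% cases", and the synopsis legend says the rate "is the expected proportion in the placebo group – 10" per cent. The legend under the formula in 9.2 gives 5% instead. The margin is 5 points, and the result is 24 completers, 26 randomised and 30 screened per group.

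The decision rule (9.1.2) first says that "unilateral statistical criteria will be used, and the level of significance will be established at 5" per cent. It then says that for each dose against placebo "a bilateral 95% binominal accurate confidence interval will be calculated for percentage difference", and: "Superiority will be confirmed, if the lower limit of the confidence interval will exceed 0.05 (5" per cent). Section 9.2 does not connect its power to this rule. Section 9.1 describes itself as a summary and leaves the full analysis to the statistical analysis plan.

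**The concern.** The power statement and the success rule are both fixed in the protocol, but they concern different statistics. For a difference of two proportions, exact does not pick out one interval. An exact unconditional interval needs a rule for ordering the possible tables. Two rules fit the words of 9.1.2: ordering on the raw difference, or on the difference standardised by its score (restricted maximum likelihood) standard error. Both guarantee the error rate. The raw-difference version takes its worst case near response rates of 50%, whatever rates are observed, so it is needlessly conservative when the placebo rate is low.

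At stake is whether 24 per group carries the stated power, and whether the same data could pass or fail according to which exact interval is run.

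**Working it through.** **Inputs.** Active rate 45%, placebo rate 10%, margin 5 points, alpha 5% through a one-sided quantile, power 80% (9.2 and synopsis); 24 completers per arm. The placebo arm is taken as unpooled, because 9.2 does not say whether the two placebo volumes are combined.

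**Step 1: reproduce the plan's figure.** n = [p1(1−p1) + p0(1−p0)] × ((z₁₋α + z₁₋β)/(p1 − p0 − δ))².

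- Variance term: 0.45×0.55 + 0.10×0.90 = 0.3375.
- (1.645 + 0.842)² / 0.30² = 68.70.
- n = 0.3375 × 68.70 = 23.18, so 24. The plan's figure reproduces at p0 = 10%.
- The formula as printed has p1(1−p0) in its first term. It gives 34.0 at p0 = 10%, and 23.97 (also 24) at the legend's 5%.

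**Step 2: normal-approximation power at 24 per arm.** 0.30/√(0.3375/24) = 2.530.

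- One-sided 5%: Φ(2.530 − 1.645) = 81.2%.
- Lower limit of a two-sided 95% interval: Φ(2.530 − 1.960) = 71.6%.

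**Step 3: power of the exact rules.** All 25 × 25 tables were enumerated. The exact one-sided p-value against a difference of 0.05 was maximised over the nuisance rate on a grid, and the binomial probabilities of the winning tables were summed at 45% v 10%.

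| Rule, 24 v 24 | One-sided 5% | Two-sided 95% limit |
|---|---|---|
| z formula | 81.2% | 71.6% |
| Exact, score ordering | 78.6% | 68.4% |
| Exact, raw-difference ordering | 62.7% | 48.9% |
| Maximum type I error, score | 4.93% | 2.47% |
| Maximum type I error, raw difference | 3.33% | 1.65% |

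Inverting the score test over differences below 0.05 as well gave the same 78.6% and 68.4%, so these are the power of the interval rule and not only of the test at the margin.

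**Step 4: separate the sources of loss.**

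- Exactness (z to score): 81.2 − 78.6 = 2.6 points, and 71.6 − 68.4 = 3.2 points.
- Construction (score to raw difference): 78.6 − 62.7 = 15.9 points, and 68.4 − 48.9 = 19.5 points.
- Level (one-sided 5% to the 95% limit, z formula): 81.2 − 71.6 = 9.6 points. This is the separate alpha conflict.

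**Step 5: what wins.** With the raw-difference interval at two-sided 95%, the smallest winning difference is 9/24 = 37.5 points. 11/24 v 2/24 has lower limit 0.075 and passes; 10/24 v 2/24 (33.3 points) has lower limit 0.032 and fails. At one-sided 5% the same 33.3 points passes (0.077). With the score-based exact interval, 10/24 v 2/24 (p = 0.012) and 11/24 v 3/24 (p = 0.018) both pass at one-sided 2.5%. For 2/24 on placebo at the 95% limit, the score version needs 9/24 active responders and the raw-difference version 11/24.

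**Step 6: other readings.** Power at one-sided 5% / two-sided 95% limit:

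| Scenario | Score | Raw difference |
|---|---|---|
| 26 v 26, p0 = 10% | 81.2% / 70.7% | 70.8% / 58.3% |
| 24 v 24, p0 = 5% | 92.6% / 86.7% | 78.6% / 66.2% |
| 24 v 48 (pooled placebo), p0 = 10% | 86.7% / 71.4% | 79.0% / 66.7% |
| 26 v 26, p0 = 5% | 93.5% / 88.3% | 85.3% / 75.5% |

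The score version has more power in every row.

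**The case against.** The strongest reply is that which exact interval to invert is ordinary statistical analysis plan detail. Section 9.1 defers the full analysis there, and the score-based interval already fits the wording of 9.1.2. That stands as far as the ordering goes: leaving it unnamed is not by itself an error, and a reader who infers that the protocol commits to the raw-difference interval, and hence to 49–63% power, goes beyond the text. It does not dispose of the mismatch, because the success rule and the 80% are both stated in the protocol.

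It is also fair to say that exactness itself costs little. At the one-sided 5% used for sizing, the score-based interval is within 2 points of 80%, and with the 26 randomised per arm it is above it. The large loss needs the raw-difference ordering, and the 48.9% also contains the alpha conflict.

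A reader might further infer that a trial observing exactly its planned effect would fail. The documents do not support this. A 35-point difference cannot occur with 24 per arm, and the planned rates rounded to whole patients, 11/24 v 2/24, pass under every rule examined. What fails is the next attainable difference below plan, and only with raw-difference ordering at the two-sided 95% limit.

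**Conclusion.** The point holds in this form: the 80% in 9.2 is not the power of the rule in 9.1.2, and the words of that rule admit intervals of very different power. At 24 v 24 and 45% v 10%, neither exact construction examined reaches 80%. The score version comes close at one-sided 5% (78.6%) and falls to 68.4% at the limit as written; the raw-difference version gives 62.7% and 48.9%. The part attributable to construction is 16 to 20 points, with no gain in error control beyond the guarantee that both share.

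The sizes rest on p0 = 10%, 24 per arm and an unpooled placebo. If the placebo rate is 5%, as the 9.2 legend has it, the score version exceeds 80% at both levels, and the raw-difference version does so at one-sided 5% with 26 per arm. The shortfall against 80% is therefore not universal; the advantage of the score version held in every scenario checked. The alpha conflict should be handled as its own point and not counted here.

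**What to change.** In 9.1.2, replace the phrase for the interval with: exact unconditional confidence interval for the difference in proportions, obtained by inverting the score statistic (Chan-Zhang). In 9.2, restate the power of 24 completers per group for that rule: about 79% if the level is one-sided 5%, about 68% if the two-sided 95% limit is kept, with the placebo rate on which it rests.

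The cost is one sentence in 9.1.2 and a restated figure in 9.2. The error guarantee is kept and no patients are added. No change to 9.1.3 is needed: the secondary comparisons use Fisher's exact test and carry no margin rule or power claim. If the sponsor wants 80% under the named interval, over the range checked (up to 47 per arm) it holds from about 26 per arm at one-sided 5% and about 34 at the two-sided 95% limit. The first equals the number already planned for randomisation.
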